14.1.4 Statistical Considerations

All questionnaires will be scored according to published scoring algorithms. The primary analysis will involve a mixed model of the EORTC QLQ-C30 HRQL summary score within each patient cohort. The mixed model will compare the post-randomization HRQL between randomized arms. In addition to a randomized arm covariate, each model will include a covariate for baseline HRQL and will use the planned month of assessment as the categorical time value. Unstructured covariance will initially be used, though alternative covariance structures will be investigated with the final covariance structure

selected based on minimization of the Akaike information criterion. The statistical significance of the randomized arm covariate between arms will be employed for hypothesis testing. Within this model, this covariate represents the estimated average difference between randomized arms across post-randomization time points. We have chosen this approach to reduce the number of hypothesis tests to one for each patient cohort. We feel that this is a reasonable approach because we anticipate a consistent effect across time points. In supplemental analysis, we will modify this approach to include a time-by-arm interaction effect and report time-specific comparisons between arms as well as model-based estimation of the area-under-the-curve throughout treatment based on mixed model contrasts.

Primary patient-reported outcome analysis will be conducted at the time that all consented patients have completed 24 weeks of treatment (or are no longer being followed for quality of life). Release of the data for presentation will be at the discretion of the DSMB. Patients will be analyzed according to the randomized treatment arm assignment. All patients who consent for participation in the HO1 component with a baseline endpoint value and at least one endpoint value post-randomization will be included in the primary analysis. In the primary analysis, all observations available will be used. See below for information regarding analyses to account for missing data.

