In secondary analysis, similar mixed model comparisons of EORTC QLQ-GI.NET21 scale scores will be conducted within each patient cohort. Graphical procedures will include plots of average values over time by arm for each primary and secondary endpoint. Exploratory analysis will include computation of Pearson correlations among patient-reported endpoints at fixed time points and univariate and multivariate linear mixed models of EORTC QLQ-C30 Global Health Status/Quality of Life score to investigate the impact of symptoms and functioning on quality of life.

Possible symptom response endpoints will be explored. Candidate summary scores include the average of all EORTC QLQ-GI.NET21 scale scores and the average of all EORTC QLQ-GI.NET21 scale scores excluding treatment-related side effects and communication. Meaningful change for each will be explored using common distribution-based and anchorbased approaches. Data will be pooled across patient cohorts for this analysis. For distribution-based approaches, meaningful changes will be estimated as 0.5 and 0.3 times the baseline standard deviation, 12-week standard deviation, 24-week standard deviation, standard deviation of the change-from-baseline scores at 12 weeks, and standard deviation of the change-from-baseline scores at 24 weeks. The anchor-based approach will employ the global impression of change items at 12 and 24 weeks. Candidate symptom response endpoints with triangulated meaningful change criteria will be applied to each treatment arm and rates of symptom response will be compared between arms within each patient cohort using a chi-squared test. Finally, cumulative distribution plots will be used to visually simultaneously assess arm comparisons across all possible meaningful change criteria within each patient cohort.

For all statistical analyses, p-values <0.05 will be considered statistically significant (though interpretation will take into consideration that the type I error is not strictly controlled across primary and secondary endpoints). For interpreting the clinical significance of effects, 0.2, 0.5, and 0.8 standard deviation (SD) effects will be considered as small, moderate, and large based on Cohen throughout [45].

Missing data will be handled in a number of ways. Missing items within a summary or scale score will be handled according to each questionnaire's published scoring algorithms. Missing data at the summary or scale score level will be handled as follows. Baseline

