patient/disease characteristics will be compared between patients who do and do not provide data for the primary analysis. We will also graphically explore patterns of missing data. All analyses will be completed using all available data, followed by analyses completed using a range of imputation methods. Lastly, we will employ pattern mixture models for longitudinal analyses. Output from all analyses will be tabulated and descriptively compared to assess the degree to which missing data impacts study results.

Power

Within the **pancreatic NET cohort**, we assume that 138 of the 185 enrolled patients will be progression-free at 12 weeks (based on median PFS of 5 months in the placebo arm and 8.8 months in the cabozantinib arm). Allowing up to 15% additional missing data due to non-compliance, we based power estimation on having baseline and at least one follow-up assessment in 117 patients (83 on the cabozantinib arm, 34 on the placebo arm) in this cohort. The primary analysis in this cohort has 80% and 90% power to detect a 0.58 and a 0.67 standard deviation difference between arms, respectively, assuming no correlation between baseline and follow-up HRQL (conservatively based on a power calculation for a two-sample t-test). With correlation of 0.5 between baseline and a single follow-up HRQL, the detectable effect size shrinks to 0.52 and 0.61, respectively, which can still be thought of as a conservative estimate based on a single follow-up time point.

Within the **carcinoid tumor cohort**, we assume that 169 of the 210 enrolled patients will be progression-free at 12 weeks (based on median PFS of 7 months in the placebo arm and 12 months in the cabozantinib arm). Allowing up to 15% additional missing data due to non-compliance, we based power estimation on having baseline and at least one follow-up assessment in 143 patients (100 on the cabozantinib arm, 43 on the placebo arm) in this cohort. The primary analysis in this cohort has 80% and 90% power to detect a 0.51 and a 0.60 standard deviation difference between arms, respectively, assuming no correlation between baseline and follow-up HRQL (conservatively based on a power calculation for a two-sample t-test). With correlation of 0.5 between baseline and a single follow-up HRQL, the detectable effect size shrinks to 0.47 and 0.55, respectively, which can still be thought of as a conservative estimate based on a single follow-up time point.

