The planned analyses will incorporate all available data to maximize power. Thus, we anticipate having 80% power for detecting an effect size between 0.4 and 0.5 standard deviations within each cohort which is considered as clinically meaningful based on the work of Cohen.

Overall power across both cohorts is expected to be 81% (i.e. $0.90 \times 0.90 = 0.81$) for effect sizes of 0.67 and 0.60 in the pancreatic NET and carcinoid tumor cohorts, respectively, assuming no correlation between baseline and follow-up HRQL, and for effect sizes of 0.61 and 0.55 in the pancreatic NET and carcinoid tumor cohorts, respectively, assuming a correlation of 0.5 between baseline and follow-up HRQL. These effect sizes are considered moderate to large and clinically-meaningful based on the work of Cohen.

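### The quality-of-life detectable effects printed for a baseline correlation of 0.5 do not follow from the plan's own inputs; the error is small and conservative

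*Combined protocol and SAP*

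**What the plan says.** All of this is in the combined protocol and SAP, Section 14.1.4 (Statistical Considerations of the quality-of-life substudy).

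- **Model.** The primary analysis is a mixed model within each cohort in which "each model will include a covariate for baseline HRQL and will use the planned month of assessment as the categorical time value".
- **Significance level.** "For all statistical analyses, p-values <0.05 will be considered statistically significant". No sidedness is given.
- **Evaluable patients.** Pancreatic NET: "117 patients (83 on the cabozantinib arm, 34 on the placebo arm"). Carcinoid: "143 patients (100 on the cabozantinib arm, 43 on the placebo arm").
- **Zero correlation.** From a two-sample t-test, the pancreatic NET cohort has "80% and 90% power to detect a 0.58 and a 0.67 standard deviation difference between arms". The carcinoid values are 0.51 and 0.60 SD.
- **Correlation 0.5, one follow-up.** Pancreatic NET: "With correlation of 0.5 between baseline and a single follow-up HRQL, the detectable effect size shrinks to 0.52 and 0.61". Carcinoid: "the detectable effect size shrinks to 0.47 and 0.55". The plan calls these conservative because they use only one follow-up time point.
- **Joint power.** The last paragraph gives 81% (0.90 x 0.90) for 0.67 and 0.60 SD at zero correlation, and again "for effect sizes of 0.61 and 0.55 in the pancreatic NET and carcinoid tumor cohorts" at correlation 0.5.

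No formula is given for the step from correlation 0 to correlation 0.5.

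**The concern.** With one follow-up and the baseline value as a covariate, a correlation of 0.5 leaves a residual SD of sqrt(1 - 0.25) = 0.866 of the unadjusted SD. Detectable effects should therefore fall by about 13%. The printed ones fall by only 8% to 10%. If the figures are wrong, the stated power and effect pairs for the primary quality-of-life endpoint are wrong in both cohorts, and so is the second half of the joint-power sentence. What is at stake is whether a reader can reproduce the substudy's stated power from its stated assumptions. The trial's sample size is not at stake, because it is set by PFS in Section 13.2.

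**Working it through.** **Inputs (Section 14.1.4).** Arm sizes n1:n2 = 83:34 and 100:43; alpha 0.05; baseline HRQL as covariate; correlation r = 0.5; one follow-up. Two-sided testing is assumed, and step 1 supports it.

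**Formula.** The detectable difference d, in SD units, solves noncentral-t power = 0.80 or 0.90, with noncentrality d / (s x sqrt(1/n1 + 1/n2)). For the t-test, s = 1 and df = N - 2. For the baseline-adjusted comparison, s = sqrt(1 - r^2) and df = N - 3. Here sqrt(1/83 + 1/34) = 0.2036 and sqrt(1/100 + 1/43) = 0.1824.

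**Step 1: the plan's zero-correlation figures.**

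| Cohort | Computed 80% / 90% | Printed |
|---|---|---|
| Pancreatic NET | 0.575 / 0.666 | 0.58 / 0.67 |
| Carcinoid | 0.514 / 0.595 | 0.51 / 0.60 |

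All four reproduce. This confirms the arm sizes, the test and two-sided 0.05 (or its one-sided 0.025 equivalent).

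**Step 2: correlation 0.5, s = 0.866.**

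| Cohort | Computed 80% / 90% | Printed |
|---|---|---|
| Pancreatic NET | 0.498 / 0.577 | 0.52 / 0.61 |
| Carcinoid | 0.446 / 0.516 | 0.47 / 0.55 |

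None of the four reproduces. To two decimals the computed values are 0.50 / 0.58 and 0.45 / 0.52.

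**Step 3: can rounding explain it?** The ratio of the correlation-0.5 figure to the zero-correlation figure should be close to 0.866, whatever the alpha. The printed ratios are 0.52/0.58 = 0.90, 0.61/0.67 = 0.91, 0.47/0.51 = 0.92 and 0.55/0.60 = 0.92. Taking every rounding limit in the plan's favour, the lowest possible ratios are:

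- 0.515/0.585 = 0.880
- 0.605/0.675 = 0.896
- 0.465/0.515 = 0.903
- 0.545/0.605 = 0.901

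All exceed 0.866.

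**Step 4: power at the printed effects, r = 0.5.**

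| Cohort | Printed effects | Nominal | Noncentral t | Simulated ANCOVA (40,000 replicates) |
|---|---|---|---|---|
| Pancreatic NET | 0.52 / 0.61 | 80% / 90% | 83.2% / 92.9% | 83.0% / 92.7% |
| Carcinoid | 0.47 / 0.55 | 80% / 90% | 84.0% / 93.3% | 83.6% / 93.1% |

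**Step 5: joint power.** At 0.61 and 0.55 it is 0.929 x 0.933 = 0.87, not 0.81.

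**Step 6: the corrected values.** Simulated power is 79.7% / 90.0% at 0.50 / 0.58 and 80.6% / 90.2% at 0.45 / 0.52.

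**The case against.** **The method is not stated, so another one may have been used.** This stands as a caveat. A change-score analysis at r = 0.5 does not help with the stated arms: its SD is sqrt(2(1 - 0.5)) = 1, so nothing would shrink. A t-test with SD 1 and equal whole-patient arms (58 per arm from 117, 71 per arm from 143) gives 0.525 / 0.607 and 0.473 / 0.548, which match all four printed values. That contradicts the 83:34 and 100:43 split stated in the same paragraphs and omits the baseline covariate of the planned model. It is a possible origin, not a justification, and the documents do not confirm it.

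**A reader might infer that a correlation near 0.4 was really used.** The documents do not support this. At r = 0.4 the model gives 0.527 / 0.610 and 0.471 / 0.546, so the first value rounds to 0.53, not the printed 0.52. At r = 0.41 the last is 0.543, which rounds to 0.54, not 0.55. Allowing for rounding, 0.52 needs a correlation of at least 0.409 and 0.55 needs at most 0.402, so no single correlation yields all four.

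**The plan already calls the figures conservative.** It attributes this to using one follow-up. The check above also uses one, so that does not explain the gap.

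**The consequence is slight.** This stands. The error overstates the detectable effect and understates power. The plan's expectation of 80% power for an effect between 0.4 and 0.5 SD is consistent with the corrected 80% values of 0.50 and 0.45. The corrected 90% values, 0.58 and 0.52, still exceed the 0.5 SD that the plan calls moderate.

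**Conclusion.** Wrong as written, but a minor and conservative error in an optional substudy. The four correlation-0.5 effects should be 0.50 / 0.58 SD (pancreatic NET) and 0.45 / 0.52 SD (carcinoid). The plan understates power by about 3 to 4 points per cohort and by about 6 points jointly (87% against 81%).

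This rests on two-sided 0.05, which the zero-correlation figures imply, on the stated arm sizes, and on a baseline-adjusted comparison with a single follow-up.

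A reader might infer that the substudy's power case or the 81% figure collapses. Neither does. The zero-correlation figures are correct, and 81% is simply 0.90 x 0.90. It holds for 0.67 and 0.60 at zero correlation, and would hold at correlation 0.5 once paired with the right effects. Only its pairing with 0.61 and 0.55 is wrong. The PFS design in Section 13 is untouched.

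**What to change.** In the Power paragraphs of Section 14.1.4:

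1. Pancreatic NET: replace 0.52 and 0.61 with 0.50 and 0.58.
2. Carcinoid: replace 0.47 and 0.55 with 0.45 and 0.52.
3. Overall-power sentence: replace 0.61 and 0.55 with 0.58 and 0.52, so that 0.90 x 0.90 = 81% holds at correlation 0.5.
4. Add one line giving the method: two-sided 0.05, baseline as covariate, residual SD sqrt(1 - r^2). If the sponsor did use another method, state it and reconcile it with the unequal arms and the covariate model.

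Do not change the stated correlation to 0.4: it would not reproduce the printed 0.52, and it would alter a design assumption to fit a printed number.

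The cost is a text correction only. No sample size, data collection, test, decision rule or PFS figure changes.

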14.2 Population Pharmacokinetics of Cabozantinib (Alliance A021602-PP1)

14.2.1 Background

The absolute bioavailability of cabozantinib tablet or capsule formulations has not been determined. As noted by Lacy et al., the median time to maximum plasma concentration (T_{max}) values across healthy volunteer (HV) studies was 3 to 5 hours, although individual subjects did show prolonged absorption phases with maximum plasma concentration (C_{max}) occurring as late as 120 hours after dosing [46]. Following the absorption peak, plasma concentrations declined slowly with a mean terminal half-life of 111–131 hours across the

studies. Cabozantinib accumulates approximately fivefold by day 15 following daily dosing based on area under the plasma concentration-time curve (AUC). A population pharmacokinetics (PK) analysis was performed on pooled data for 289 cabozantinib-treated cancer patients (including medullary thyroid cancer [MTC]) receiving daily administration of the cabozantinib capsule formulation at a dose of 140 mg FBE/day (FBE, free base equivalents), except for five subjects that were dosed at 200 mg FBE/day. The data were adequately described by a one-compartment model with first-order absorption and first-order elimination with a small lag time. The mean clearance of distribution (CL/F) and apparent volume of distribution (Vc/F) were estimated to be 106 L/day (standard error % [SE%] = 2.98%) and 349 L (SE% = 2.73%), respectively, resulting in an estimated effective half-life of 2.28 days (55 hours).

Hepatobiliary elimination appears to be the major route of elimination of cabozantinib and its inactive metabolites, while urinary excretion is a route of elimination exclusively for cabozantinib metabolites. Four identified inactive metabolites constitute approximately 65% of total cabozantinib-related AUC following a single 140-mg FBE dose.

The protein binding of cabozantinib is approximately 99.77%. The percentage of cabozantinib unbound to plasma protein appeared to be correlated with serum albumin concentration; subjects with low serum albumin concentrations exhibited a higher percentage of unbound plasma protein and lower total C_{max} . The mean values of systemic exposures, AUC_{0-24} and AUC_{0-72} , in plasma were around 1.6 times higher than those in whole blood.

Single doses of cabozantinib tablets at 20-, 40-, and 60-mg FBE dose strengths showed dose-proportional increases in mean plasma cabozantinib C_{max} and AUC_{0-t} values, suggesting linear pharmacokinetics.

Cabozantinib AUC was increased by 63-81% or 7-30% in subjects with mild/moderate hepatic or renal impairment, respectively, by 34-38% with concomitant administration of the CYP3A4 inhibitor ketoconazole, and by 57% following a high-fat meal. Cabozantinib AUC was decreased by 76-77% with concomitant administration of the CYP3A4 inducer rifampin and was unaffected following administration of the proton pump inhibitor esomeprazole. Cabozantinib is a potent *in vitro* inhibitor of P-glycoprotein and multidrug and toxin extrusion transporters 1 and 2-K, and it is a substrate for multidrug resistance protein 2.

Patients with medullary thyroid cancer with low model-predicted apparent clearance were more likely to dose hold/reduce cabozantinib early and had a lower average dose through day 85. However, longitudinal tumor modeling suggests that cabozantinib dose reductions from 140 to 60 mg/day did not markedly reduce tumor growth inhibition in medullary thyroid cancer patients.

PK parameter values at a single 140-mg FBE dose were generally consistent for capsule and tablet formulations administered in HVs and for the capsule formulation administered in subjects with advanced malignancies.

In a population pharmacokinetic analysis, no clinically significant covariates affecting cabozantinib pharmacokinetics were identified. Sex and body mass index (BMI) on oral clearance were the only covariates retained in the final model. Cabozantinib CL/F was shown to decrease by approximately 22% at the 95th percentile of BMI relative to the median, which translates to an approximately 28% increase in steady-state AUC. Female individuals cleared cabozantinib slower than male individuals by 22%, resulting in a predicted increase in steady-state AUC of 28% for female individuals. Sex and BMI

combined contributed to 15% of the variability in cabozantinib CL/F. Cabozantinib pharmacokinetics were not affected by age (20-86 years). The effect of race on cabozantinib pharmacokinetics could not be concluded based on the low percentages of non-white patients in the study population. Inter-individual variability in CL/F was modest (coefficient of variability [CV] = approximately 35%).

The inter-subject variability (%CV) in HVs following a single capsule or tablet dose ranged from 20-59% for AUC values and from 28-72% for C_{max} values across the studies. The %CV was estimated to be 39% for C_{max} and 28% for AUC values in the capsule-tablet bioequivalence study. The %CV in cancer patients was 42-43% for C_{max} and 34% for AUC after a single dose, and 37-43% for C_{max} and 38-43% for AUC at steady state.

In the pivotal phase III study for MTC, 79% of patients who received the 140-mg FBE cabozantinib dose eventually dose reduced. Forty-two percent of subjects received 60 mg/day as their final dose. Exposure-response analyses showed an increased risk for time-to-first-cabozantinib-dose-modification to be highly correlated with higher AUC_{ss, pred}. However, Kaplan–Meier analyses of progression-free survival (PFS) stratified by time-to-first-dose-modification (tertiles) showed no clear association between early and late cabozantinib dose modifications and reduced PFS. These findings suggest that, although MTC patients who clear cabozantinib slower may have a higher risk of early dose reduction relative to the faster-clearing patients, the dose reduction paradigm used in the phase III study allowed individual MTC patients to ultimately attain a tolerated exposure providing clinical benefit [46].

14.2.2 Objectives

To determine the intra-patient and inter-patient variability of cabozantinib exposure (C_0) in patients with advanced neuroendocrine tumors receiving cabozantinib.

To correlate cabozantinib exposure (C_0) and AUC, as determined by population pharmacokinetic analysis, with toxicity and efficacy in patients with advanced neuroendocrine tumors.

14.2.3 Methods

Approximately 5 mL of peripheral blood for cabozantinib trough concentrations will be obtained from consenting patients prior to receiving their first cabozantinib dosage on Cycle 1 Day 1 and then obtained during clinic visits on Cycle 1 Day 15, Cycle 2 Day 1, Cycle 2 Day 15, and Cycle 3 Day 1 while still on protocol therapy but before receiving the scheduled daily dose (trough sample). The time of day the samples were obtained will be documented. Plasma will be extracted by local hospitals and shipped to the Alliance Pharmacology/Pharmacokinetic Core Laboratory at the University of Pittsburgh in a frozen condition. During the clinic visits, a Patient Pharmacokinetics Form (see Appendix IV) will be completed which will collect information about the timing of the previous 48-hours of cabozantinib dosing; this will detail the time the last two doses of study drug were received.

Drug concentrations will be measured in plasma using an LC-MS/MS assay implemented by the Alliance Pharmacology/Pharmacokinetic Core Laboratory at the University of Pittsburgh using a modification of the assay published by Su et al. [47].

Both frequentist and population modeling approaches will be employed.

14.2.4 Analyses

For the first objective, we will calculate the intra- and inter-subject variability in exposure. Population pharmacokinetic approaches will be employed to achieve this.

For the second objective, population pharmacokinetic approaches will be used to explore the relationships of exposure versus dose modification, toxicity, and efficacy.

Factors such as patient weight, height, albumin levels, etc. will be used as covariants in the analyses.

The data collected from the samples, as outlined above, will be sent using encrypted secure spreadsheets to the Alliance SDC A021602 Statistician. Statistical analyses will be a collaboration between the Alliance SDC and Alliance Pharmacology/Pharmacokinetic Core Laboratory teams.

